Blood Chemistry ¹¹	X	X	X	X	X	X	X	X	X	X	X	X	X	
Coagulation ¹²	X	X	X	X	X	X	X	X				X	X	
Urinalysis ¹³	X			X									X	
Pregnancy test ¹⁴	X	X	X	X				X				X	X	
Hepatitis B and C testing [hepatitis B surface antigen and core antibody; anti-hepatitis C antibody]	X													
Endocrine function assessment ¹⁵	X		As clinically indicated											

Table 3. Schedule of Activities: Portion B (PF-05082566 + Rituximab) Assessments (Dose Escalation Only)

Protocol Activity (Cycle Day relative to PF-05082566 dosing)	Screen ¹	CYCLE 1						CYCLE ≥2-8 ³⁵				>Cycle 8 ^{23,26,35}	End of Treatment ³²	Follow up ³³	
	Within 28 days prior to enrollment	Day (-7) ³⁴	Day (0)	Day 1	Day 7	Day 14	Day 22	Day 1 (± 2)	Day 8 (± 2)	Day 15 (± 2)	Day 22 (± 2)	Day 1 (± 2)			
LVEF assessment ¹⁶	X	As clinically indicated													
Registration and Treatment															
Registration ¹⁷		X													
Administration of PF-05082566 ¹⁸				X				X				X			
Administration of Rituximab ¹⁹		X	X		X	X									
Tumor assessments				X											
CT or MRI scan or equivalent ²⁰	X							To be assessed approximately every 8 weeks (±1 week) for the first 10 months on study treatment, then subsequently every 16 weeks (±1 week)				X	X		
Other clinical assessments															
AEs ²¹		Monitored and Recorded Continuously										X			
Review Prior/Concomitant Medication ²²	X	Monitored and Recorded Continuously										X	X		

Table 4. Schedule of Activities: Portion B (PF-05082566 + Rituximab: Dose Escalation Only): Pharmacokinetic, CCI CCI CCI Assessments

Assessments (Cycle Day relative to PF-05082566 dosing)	Cycle 1							Cycle 2				Cycle 3		Cycle 4		Cycle >4	End of Treat- ment ³²	Follow up ³³	
	Day (-7)	Day (0)	Day 1	Day 3	Day 7	Day 14	Day 22	Day 1 (±)2	Day 8 (±)2	Day 15 (±)2	Day 22 (±)2	Day 1 (±)2	Day 22 (±)2	Day 1 (±)2	Day 28 (±)2	Day 1 (±)2			
Blood for PF-05082566 PK ²³			X	X	X	X	X	X	X	X	X	X	X	X	X	X	X	X	
Blood for Rituximab PK ²⁴	X	X	X	X	X	X	X	X		X								X	
CCI			█	█	█	█	█	█	█	█	█	█	█	█	█	█		█	
CCI	█		█	█	█	█		█	█	█		█	█	█	█	█		█	
Blood for PF-05082566 Immunogenicity (ADA) testing ²⁷			X					X				X		X		X	X	X	
Blood for Rituximab immunogenicity (ADA) testing ²⁸	X	X			X	X				X								X	
CCI			█							█									
CCI			█					█											
CCI			█																
CCI			█					█											

Footnotes for Schedule of Activities – Portion B (PF-05082566 + Rituximab) Table 3 and Table 4.

1. Screening: To be performed within 28 days prior to enrollment (Pfizer signature of the enrollment form).

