33. Follow up period: Patients should be evaluated for adverse events up to 60 days after last dose of study treatment. Patients continuing to experience toxicity at this point will continue to be followed at least every 4 weeks until resolution or determination, in the clinical judgment of the Investigator, that no further improvement is expected. Immunogenicity (ADA) samples should be collected beyond 28 days for patients who are positive for ADA (Refer to Footnote 27). During the follow-up phase, Immunogenicity (ADA) samples should be collected at the same time as disease assessments are being performed until ADA levels return to baseline or until the patient enters the survival follow phase. Thereafter, patients whose disease has not progressed at the end of treatment will enter into disease follow-up. During this follow-up period, patients will have disease assessments performed every 16 weeks (± 1 week). Once patients have exhibited disease progression, they will enter into survival follow-up for assessment of survival only. A new anti-cancer therapy will be reported on the CRF. Survival follow-up will be conducted within 12 weeks (+/- 4 weeks) from the last survival follow-up for up to 2 years from first dose of study treatment for the last enrolled patient (telephone calls acceptable).
34. For infusion reactions to rituximab where a partial dose (<50% of the full dose) is administered, either the Day -7 dose OR the Day 0 administration of Cycle 1 and the associated procedures may be repeated one time based on the rituximab label guidelines, local practice, and eligibility for retreatment as detailed in Section 5.4.
35. For patients continuing on study beyond 8 cycles of therapy, continued treatment will be on a reduced visit schedule (Day 1 of each cycle), or as clinically indicated, until disease progression, unacceptable toxicity, or withdrawal of consent up to a maximum of 2 years from the first dose of study drug.

CCI

Table 5. Schedule of Activities for Expansion Cohorts (Portions A and B)

Protocol Activity (Cycle Day relative to PF-05082566 dosing)	Screen ¹	CYCLE 1					CYCLE ≥2	End of Treatment ²	Follow up ³
	Within 28 days prior to randomization OR enrollment	Day -7 ⁴ (Portion B Only)	Day 0 ⁴ (Portion B Only)	Day 1	Day 7 (Portion B Only)	Day 14 (Portion B Only)	Day 1 (±) 2		
Informed Consent	X								
Tumor History ⁵	X								
Medical History ⁶	X								
Physical Examination ⁷	X	X		X			X	X	
ECOG Performance Status ⁸	X	X		X			X	X	

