5.1. Allocation to Treatment

5.1.1. Allocation to Treatment for Patients Enrolled in the Randomized Expansion Cohorts of Portion A

Allocation of patients with advanced melanoma to treatment groups will proceed through the use of an interactive response technology (IRT) system (interactive Web based response [IWR]). The site staff (study coordinator or specified designee) will be required to have an active or valid account and password with the IRT system, enter or select information including but not limited to the protocol number, specific protocol entrance criteria indicated in the system and the screening number. The site staff will then be provided with, at a minimum, a treatment assignment and a randomization number. The IRT system will provide a confirmation report containing the patient number and the randomization number. The confirmation report must be stored in the site's files. The study specific IRT reference manual will provide the contact information and further details on the use of the IRT system.

Eligible patients will be randomized in a 2:1:1 ratio to receive PF-05082566 at the 0.6, 0.24 or 1.2 mg/kg dose levels, respectively. Study treatment must start within 3 days after patient randomization.

There is a 24-hour-a-day, 365-days-a-year IRT helpdesk available for any questions or issues. The study-specific IRT reference manual will provide the contact information and further details on the use of the IRT system.

5.1.2. Allocation to Treatment for Patients Enrolled in the Non Randomized Expansion Cohorts of Portion A and Portion B

Dose level allocation will be performed by the Sponsor after patients have given their written informed consent and have completed the necessary baseline assessments. The site staff will (fax or/and email) a complete Registration Form to the designated Sponsor study team member. The Sponsor will assign a patient identification number, which will be used on all Case Report Form (CRF) pages and other trial-related documentation or correspondence referencing that patient and (fax or/and email) to the site.

No patient shall receive the investigational products until the Investigator or designee has received the following information in writing from the Sponsor:

- Confirmation of the patient's enrollment;
- Specification of the dose level for that patient;
- Permission to proceed with dosing the patient.

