Appendix 2. Determination of Efficacy – Solid Tumors

CATEGORIZING LESIONS AT BASELINE

Measurable Lesions

- Lesions that can be accurately measured in at least one dimension.
- Lesions with longest diameter twice the slice thickness and at least 10 mm or greater when assessed by CT or MRI (slice thickness 5-8 mm).
- Lesions with longest diameter at least 20 mm when assessed by Chest X-ray.
- Superficial lesions with longest diameter 10 mm or greater when assessed by caliper.
- Malignant lymph nodes with the short axis 15 mm or greater when assessed by CT.

NOTE: The shortest axis is used as the diameter for malignant lymph nodes, longest axis for all other measurable lesions.

Non-measurable disease

Non-measurable disease includes lesions too small to be considered measurable (including nodes with short axis between 10 and 14.9 mm) and truly non-measurable disease such as pleural or pericardial effusions, ascites, inflammatory breast disease, leptomeningeal disease, lymphangitic involvement of skin or lung, clinical lesions that cannot be accurately measured with calipers, abdominal masses identified by physical exam that are not measurable by reproducible imaging techniques.

- **Bone disease:** Bone disease is non-measurable with the exception of soft tissue components that can be evaluated by CT or MRI and meet the definition of measurability at baseline.
- **Previous local treatment:** A previously irradiated lesion (or lesion subjected to other local treatment) is non-measurable unless it has progressed since completion of treatment.

Normal sites

- **Cystic lesions:** Simple cysts should not be considered as malignant lesions and should not be recorded either as target or non-target disease. Cystic lesions thought to represent cystic metastases can be measurable lesions, if they meet the specific definition above. If non-cystic lesions are also present, these are preferred as target lesions.
- **Normal nodes:** Nodes with short axis <10 mm are considered normal and should not be recorded or followed either as measurable or non-measurable disease.

RECORDING TUMOR ASSESSMENTS

All sites of disease must be assessed at baseline. Baseline assessments should be done as close as possible prior to study start. For an adequate baseline assessment, all required scans must be done within 28 days prior to treatment and all disease must be documented appropriately. If baseline assessment is inadequate, subsequent statuses generally should be indeterminate.

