2. INTRODUCTION

This SAP provides the detailed methodology for summary and statistical analyses of the data collected in study B1641001. This document may modify the plans outlined in the protocol; however, any major modifications of the primary endpoint definition or its analysis will also be reflected in a protocol amendment.

Statistical analyses will be performed using cleaned eCRF data as well as non-CRF data (ie, CCI data, PK data). The primary analysis will include all data up to a clinical cut-off date corresponding to 24 months (104 weeks) after the last patient is randomized (for randomized cohorts) or treated (for non-randomized cohorts). The final analysis of the data will be performed after last patient last visit (LPLV).

Additional analyses of the data may be performed for publication or regulatory reporting purposes.

Throughout this document ‘start date’ refers to date of randomization for randomized cohorts and first dose of study treatment for non-randomized cohorts.

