5.2.10. Adequate Baseline Tumor Assessment

Adequate baseline is defined using the following criteria:

- All baseline assessments must be within 28 days prior to and including ‘start date’.
- All documented lesions must have non-missing assessments (ie, non-missing measurements for target lesions (for patients with solid tumor) or index lesions (for patients with NHL) and non-missing lesions status at baseline for non-target lesions (for patients with solid tumor) or non-index lesions (for patients with NHL)).

- Computerized tomography (CT) or magnetic resonance imaging (MRI) is required at baseline and may include chest, abdomen and pelvis. Brain scans will be performed at baseline for patients with CNS disease or if disease is suspected, and on study as appropriate to follow disease. Baseline CNS imaging is not required unless to confirm stability of existing CNS metastases or for symptomatic patients to rule out CNS metastases. Bone scans will be performed at baseline if disease is suspected only for patients enrolled in Portion A, and on study as appropriate to follow disease.

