6.2.2.3. Duration of Response

Duration of Response (DR) is defined, for patients with OR, as the time from first documentation of objective response (CR or PR) to the date of first documentation of objective progression of disease (PD) or death due to any cause. If a patient has not had an event (PD or death), DR is censored at the date of last adequate tumor assessment. The censoring rules for DR are as described below for PFS in [Table 3](#).

$$\text{DR (months)} = [\text{date of event or censoring} - \text{first date of OR} + 1] / 30.4375$$

Kaplan-Meier estimates (product-limit estimates) will be presented by treatment group together with a summary of associated statistics including the median DR time with 2-sided 95% CIs. In particular, the DR rate at 3, 6 and 12 months will be estimated with corresponding 2-sided 95% CIs. The CIs for the median will be calculated according to Brookmeyer and Crowley and the CIs for the survival function estimates at the time points defined above will be derived using the log-log transformation according to Kalbfleisch and Prentice (conftype=loglog default option in SAS Proc LIFETEST) with back transformation to a CI on the untransformed scale. The estimate of the standard error will be computed using Greenwood's formula.

DR will be displayed graphically and analyzed using Kaplan-Meier methodology. If the number of patients with OR is small, the Kaplan-Meier method may not provide reliable estimates. In this case, only descriptive statistics or listings will be provided.

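### A baseline scan that is on time under the protocol can fail the SAP's 28-day rule, which censors PFS on the start date; the same SAP Table 3 row gives responders a negative DR

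*SAP*

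**What the plan says.** **Screening window.** The screening column of Protocol Table 5 (expansion cohorts) reads "Within 28 days prior to randomization OR enrollment". The dose-escalation tables also count back from enrollment, and footnote 1 to Protocol Tables 3 and 4 explains what that means: "To be performed within 28 days prior to enrollment (Pfizer signature of the enrollment form". Protocol 5.1.2 requires written confirmation of enrollment before a non-randomized patient is dosed, and sets no maximum interval. For the randomized melanoma cohort, Protocol 5.1.1 does: "Study treatment must start within 3 days after patient randomization".

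**Adequate baseline.** SAP 5.2.10 requires: "All baseline assessments must be within 28 days prior to and including" 'start date'. SAP section 2 says that this term "refers to date of randomization for randomized cohorts and first dose of study treatment for non-randomized cohorts". In Portion B, SAP 3.7.1 takes the earlier of the two drugs' first doses, which is the rituximab dose on Cycle 1 Day −7.

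**Appendix 2 (solid tumors).** The anchor here is treatment: "all required scans must be done within 28 days prior to treatment and all disease must be documented appropriately". It adds: "If baseline assessment is inadequate, subsequent statuses generally should be indeterminate". Appendix 3 (lymphoma) has no 28-day rule.

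**Consequence in the SAP.** SAP 6.2.2.5 and SAP Table 3 censor PFS on 'start date' when there is no adequate baseline, except that a death within 16 weeks remains an event. SAP Table 3 is titled for both PFS and DR, and SAP 6.2.2.3 says: "The censoring rules for DR are as described below for PFS in" that table. The sentence just before it censors DR, for responders without progression or death, at the last adequate tumor assessment.

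**The concern.** Sites follow the protocol and the analysis follows the SAP. In the non-randomized cohorts (dose escalation, non-randomized Portion A expansion, all of Portion B) the two count 28 days from different dates. A patient who broke no rule can have an observed progression replaced by censoring on the first day, so that the patient contributes almost nothing to the PFS estimate.

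The DR problem is separate and does not need a scheduling gap. SAP 5.2.10 also calls a baseline inadequate if any documented lesion lacks a baseline measurement or status, which can happen in any cohort. SAP 6.2.2.1 still allows such a patient to be a responder: its reasons for a not-evaluable best response include an absent baseline but not an inadequate one. The patient then enters the DR analysis with a censoring date that precedes the response.

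PFS and DR are secondary and descriptive, but FL-1 and FL-2 have up to 20 patients each, so one or two patients handled this way would show.

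**Working it through.** The plan gives no figure for this point, so the check is date arithmetic on its own rules.

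**Assumptions.** The Table 5 scan window is taken from its screening column header. Enrollment in the expansion cohorts is taken to mean what footnote 1 to Protocol Tables 3 and 4 says. The enrollment-to-dose gap in the non-randomized cohorts is not given; 0, 1 and 3 days are used as illustrations.

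**Step 1: which rules does a scan exactly 28 days before the protocol anchor meet?** Distance to first dose = 28 + gap.

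| Cohort | Gap to first dose | Protocol screening | SAP 5.2.10 | Appendix 2 (solid tumors) |
|---|---|---|---|---|
| Non-randomized | 0 days | 28, passes | 28, passes | 28, passes |
| Non-randomized | 1 day | 28, passes | 29, fails | 29, fails |
| Non-randomized | 3 days | 28, passes | 31, fails | 31, fails |
| Randomized | 0 days | 28, passes | 28, passes | 28, passes |
| Randomized | 1 day | 28, passes | 28, passes | 29, fails |
| Randomized | 3 days | 28, passes | 28, passes | 31, fails |

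So the SAP and the screening window conflict only in the non-randomized cohorts. In the randomized cohort they agree, and only Appendix 2 differs.

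**Step 2: share of non-randomized patients affected.** Assume the scan falls with equal chance on each of days 0 to 28 before enrollment, 29 values. With a gap of k days, the k oldest values fail, so the share is k/29:

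- k = 1: 1/29 = 3.4%
- k = 3: 3/29 = 10.3%

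**Step 3: PFS for such a patient.** PFS = (censoring date − start date + 1)/30.4375 = (0 + 1)/30.4375 = 0.03 months, whatever date progression was documented, unless the patient died within 16 weeks.

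**Step 4: DR under the same row.** DR = (event or censoring date − first response date + 1)/30.4375. With response at the first scheduled scan, 8 weeks after start (Day 57), and censoring on Day 1:

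(1 − 57 + 1)/30.4375 = −55/30.4375 = −1.8 months.

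At the edges of the ±1 week scan window, the result is −1.6 months (week 7) and −2.0 months (week 9). A response first seen at week 16 gives −3.6 months.

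**The case against.** **The gap is planned to be zero.** Registration is marked on the first dosing day: Day 1 in Protocol Table 1, Day −7 in Protocol Table 3, and both in Table 5. In Portion B the start date is also Day −7. If registration and enrollment coincide, nothing is misclassified. This stands as a limit on frequency. It does not remove the conflict, because the dates are defined separately and no maximum is set.

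**The SAP already says how to censor DR.** A sensible programmer would use the last adequate assessment. That sentence contradicts the SAP Table 3 row but does not override it, because the next sentence adopts the table. For a responder with documented progression the row also contradicts the DR definition, which counts progression as the event.

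**The remedy is a choice.** For non-randomized solid tumors, the SAP and Appendix 2 agree with each other and the screening window is the outlier; one could tighten screening instead. That is a fair alternative for future patients. It does nothing for those already screened: dose escalation was complete by June 2016, and 34 Portion A and 14 Portion B expansion patients were enrolled by September 2016.

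**No test depends on it.** SAP 5.1.1 plans no hypothesis testing. True, and it bounds the harm to descriptive estimates.

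**Conclusion.** Two defects hold. In the non-randomized cohorts, a scan that complies with the protocol can be ruled inadequate after a gap as short as one day, and PFS is then censored on the start date despite documented progression. On the even-spread assumption this reaches about 3% of patients for a 1-day gap and 10% for a 3-day gap, and none where dosing is on the day of enrollment. In any cohort, the SAP Table 3 row for an inadequate baseline, applied to DR, yields a negative duration for a responder, unless the patient died within 16 weeks.

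Three stronger readings are tempting and are not supported.

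- *Primary-endpoint responses are lost.* The SAP derives best response from the recorded assessments and never makes a patient with an inadequate baseline a non-responder. Only Appendix 2 could, for solid tumors, and its wording (generally) leaves it to judgment. One response among about 20 patients at a dose is 5 points of ORR, but that is the size of a single discretionary loss, not an expected effect.
- *Each patient faces three conflicting windows.* Enrollment, randomization and first treatment all serve as anchors somewhere, but any one patient meets at most two.
- *A quarter of patients could be affected.* That needs a 7-day gap (7/29 = 24%), which no passage supports.

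Negative DR and an unscorable response are also alternatives: DR arises only if the patient still counts as a responder.

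**What to change.** 1. In SAP Table 3, state that the row for patients without an adequate baseline applies to PFS only. State that DR without an event is censored at the last adequate assessment, and never before the response date.
2. In SAP 5.2.10, accept a baseline scan that meets the protocol screening window (within 28 days before randomization or enrollment, by cohort) and precedes first dose. Change the Appendix 2 sentence to the same anchor. With one anchor, the scan in Step 1 passes every rule whatever the gap.

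The enrollment date is already used in SAP 5.3.3.1, so the rule can be programmed. The cost is wording in two SAP places and one sentence in Appendix 2. The downside is that a few accepted baselines will be older than 28 days at first dose and, with no stated maximum gap, the rule does not cap their age. List these patients with the scan-to-dose interval so that readers can judge them.

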5.2.11. Adequate Post-baseline Tumor Assessment

An adequate post-baseline assessment is defined as an assessment where a response of CR, PR, SD, non-CR/non-PD, or PD can be determined (see [Section 6.1.2.1](#)). Time points where the response is NE or no assessment was performed will not be used for determining the censoring date.

5.3. Methods to Manage Missing Data

5.3.1. Missing Data

Unless otherwise specified, all data will be evaluated as observed, and no imputation method for missing values will be used.

In all patient data listings imputed values will be presented. In all listings imputed information will be flagged.

Missing statistics, eg, when they cannot be calculated, should be presented as ‘ND’ or ‘NA’. For example, if $N=1$, the measure of variability (SD) cannot be computed and should be presented as ‘ND’ or ‘NA’.

5.3.1.1. Pharmacokinetic Concentrations

Concentrations Below the Limit of Quantification

For all calculations, figures and estimation of individual pharmacokinetic parameters, all concentrations assayed as below the level of quantification (BLQ) will be set to zero. In log-linear plots these values will not be represented. The BLQ values will be excluded from calculations of geometric means and their CIs. A statement similar to ‘All values reported as BLQ have been replaced with zero’ should be included as a footnote to the appropriate tables and figures.

Deviations, Missing Concentrations and Anomalous Values

In summary tables and plots of median profiles, concentrations will be set to missing if one of the following cases is true:

1. A concentration has been reported as ND (ie, not done) or NS (ie, no sample);
2. A deviation in sampling time is of sufficient concern or a concentration has been flagged as anomalous by the clinical pharmacologist.

Summary statistics will not be presented at a particular time point if more than 50% of the data are missing. For analysis of pharmacokinetic concentrations, no values will be imputed for missing data.

